5.2.2 Phase II period

After the pilot phase has been completed, the phase II period will be started with the dose level in which there is ≤ 1 out of 6 patients experiencing any DLT.

5.3 General Concomitant Medication

All concomitant treatments and therapies, or medication administered during the 28 days preceding the screening study visit must be reported. The generic name of the drug (or trade name for combination drugs) must be specified along with the route of administration, dosage, frequency of dosage, and duration of treatment. Any medication which is considered necessary for the patient's welfare, and which is not expected to interfere with evaluation of the study drug, may be given at the discretion of the investigator. Patients must notify the investigator of all concomitant medications taken through completion of the study.

Throughout the study, investigators may prescribe any concomitant medications or treatments deemed necessary to provide adequate supportive care, such as potassium and phosphorus supplements and anti-emetics, with the exception of those listed below.

The following concomitant medications are prohibited:

- **Valproic acid, Zolinza™ (vorinostat), or any other HDAC inhibitor**
- **DNA methyltransferase inhibitors**
- **Other anti-cancer agents including Lupron or other approved luteinizing-hormone releasing hormone (LHRH) agonists such as goserelin or leuprolide**
- **Bisphosphonates initiated within 4 weeks prior to study start**
- **Other investigational agents**

Delay administration of H₂-antagonists, antacids, or proton pump inhibitors, or other drugs that lower acidity for at least 2 hours after dosing entinostat.

5.4 Duration of Therapy

- In the first cohort, treatment will be administered for a minimum of 15 days and up to 29 days prior to the definitive surgery. However if clinically acceptable, the preferred treatment duration is 22 days. The treatment should be continued until the time of the surgery (up to 29 days) or until one of the criteria in section 5.8 applies.
 - Anastrozole or tamoxifen treatment should be continued until the time of the surgery for a maximum of 29 days or until one of the criteria in section 5.8 applies.
 - Entinostat should be administered within 6 days prior to the definitive surgery. A minimum of 3 doses (day 1, 8, and 15) are required to complete the study.
- In the second cohort, treatment including entinostat and anastrozole/tamoxifen will be continued until disease progression. Restaging scans will be performed every 6 weeks while on treatment.

5.5 Surgical Considerations for the First Cohort (Operable Stage I-II)

5.5.1 Marker Placement Prior to Initiation of Therapy

A titanium marker or "clip" should be placed at the tumor site(s) prior to starting treatment in women who may be candidates for breast conservation surgery. This will identify the tumor location(s) for the surgical procedure in the event that there is a complete response to the preoperative treatment.

5.5.2 Breast Surgery

Following preoperative treatment, women will undergo breast conserving surgery or a mastectomy at the discretion of the treating surgeon. It is recommended that the definitive surgery take place within 6 days (preferably within 3 days) after the last dose of entinostat. Anastrozole should be continued until the day of the surgery.

5.5.3 Axillary Staging

Pre-treatment

- Fine needle aspiration (FNA) or core biopsy of an axillary lymph node is permitted for any patient.
- A pre-neoadjuvant therapy sentinel lymph node biopsy (SLNB) for patients with clinically *negative* axillary lymph nodes is permitted.

Post-treatment

- Post-neoadjuvant therapy axillary staging is required for all patients and will be performed according to the widely accepted American Society of Clinical Oncology (ASCO) guideline⁴¹.

5.6 Postoperative Treatments

5.6.1 Chemotherapy

It is recommended that postoperative chemotherapy be administered. The adjuvant chemotherapy regimen is at the discretion of the treating physicians.

5.6.2 Radiation Therapy

Radiation therapy will be administered at the conclusion of all protocol treatment, when appropriate.

5.7 Duration of Follow Up

Patients will be followed for 30 days after the last dose of study medication or until death, whichever occurs first. In patients who receive other primary treatment after entinostat and anastrozole administration and prior to surgery, we will collect a summary of the treatment given to correlate, if needed, with tissue samples from the surgical procedure – no additional data will be collected after that time. Patients continuing to experience adverse events attributable to the study drug will be followed as needed until resolution or stabilization of the adverse events. Patients who either are found to be ineligible or refuse to start treatment after consenting will not be followed and their information will not be collected.

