4. REGISTRATION PROCEDURES

4.1 General Guidelines

Eligible patients will be entered on study at the University of Maryland Greenebaum Cancer Center by the Study Coordinator. Following registration, patients should begin protocol treatment within 3 business days. All of the patients' documents must be kept confidential in a secured area.

To register a patient, the following documents should be completed by a research team member and sent to the Study Coordinator, [name] or [name], via fax, [contact], or e-mail, [contact] or [contact]

- Copy of required laboratory tests
- Signed patient consent form
- HIPAA authorization form
- Other appropriate forms (e.g., Eligibility Screening Worksheet, Documentation of Pathology and Diagnosis, Registration Form)

To complete the registration process, the Coordinator will

- Assign the patient a study number
- Register the patient on the study

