5. TREATMENT PLAN

5.1 Agent Administration

Treatment will be administered on an outpatient basis. Reported adverse events and potential risks for anastrozole and entinostat are described in Section 7. Appropriate dose modifications for entinostat and anastrozole are described in Section 6. No investigational or commercial agents or therapies other than entinostat, anastrozole, and tamoxifen may be administered with the intent to treat the patient's malignancy.

In the first cohort:

- Treatment will be continued for a minimum of 15 days and a maximum of 29 days. If clinically acceptable, treatment should be preferably continued for 22 days prior to the definitive surgery.
- Anastrozole will be administered continuously starting on day 4 at a fixed dose of 1 mg oral once daily.
- In patients who are not postmenopause as defined by any of the following criteria, tamoxifen will be administered continuously instead of anastrozole starting on day 4 at a fixed dose of 20 mg oral once daily.

Postmenopausal as defined by any of the following criteria:

- Age \geq 60
- Age < 60 with amenorrhea > 12 months and an intact uterus and an FSH and estradiol level within the postmenopausal range by institutional laboratory parameters.
- Age < 60 with previous hysterectomy must have FSH and estradiol level within the postmenopausal range by institutional laboratory parameters.
- Any age having undergone bilateral oophorectomy
- Entinostat will be administered at the assigned dose once a week (on day 1, 8, 15, 22, and 29) until the definitive surgery. Entinostat should be taken with a meal after the first two or three bites.
 - The initial starting dose for entinostat is 5 mg oral weekly. Dose de-escalation to 3 mg/week is permitted in the pilot phase if dose limiting toxicity is observed as defined in section 5.2.1.
 - Dose level for entinostat in phase II part of this study will be determined after the pilot phase is completed.

In the second cohort:

1. Pretreatment biopsy (biopsy#1) will be performed within 3 weeks after registration. However, the pretreatment biopsy can be omitted in patients who have recent biopsy but have not been started on breast cancer treatment within 12 weeks prior to the registration and there is adequate tumor tissue sample as per section 3.1.9.

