7.1 Adverse Events (AEs)

An Adverse Event is any untoward occurrence reflecting a change from baseline state after signing informed consent and up to 30 days from last administration of the study medication. A Serious Adverse Event (SAE) is any AE that is 1) Fatal, 2) Life Threatening, 3) Requires or prolongs hospital stay, 4) Results in a persistent or significant disability or incapacity. 5) Results in a congenital anomaly or birth defect or 6) Is considered by the Investigator as an important medical event.

7.1.1 The descriptions and grading scales found in the revised NCI Common Terminology Criteria for Adverse Events (CTCAE) version 4.0 (Available through <http://ctep.cancer.gov>) will be utilized for AE reporting. AEs of any grade will be documented in the case report form.

7.1.2 AEs can be “Expected” if described in the Informed Consent or “Unexpected”. The attribution of the AE is Definite if the AE is clearly related to study treatment; Probable if it is likely related to the study treatment; Possible if it is equally likely related to study treatment or to some other circumstance, and Unlikely if most probably some other event was responsible for the adverse event, and Unrelated if the Adverse Event is entirely explained by circumstances not caused by the study medication.

7.1.3 Data Safety Monitoring. The UMGCC Data Safety Monitoring / Quality Assurance Committee will review the study. The specific functions of the DSMB /QAC are contained in the UMGCC Clinical Investigators Handbook, available through http://www.umgcc.org/research/clinical_research.htm which is modeled closely after NCI policies and procedures for example, for adverse event reporting. (See <http://www.ctep.nci.nih.gov>.)

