9.1.1 Collections

In the first cohort:

Tumor tissue samples from the following time points will be obtained:

1. Prior to starting treatment or tissue sample at the original diagnostic procedure. (T0)
2. At the time of definitive surgery (i.e., mastectomy or lumpectomy). A separate tumor biopsy is not needed on the day of surgery; tissue will be taken from the surgical specimen. (T1)

Note: If a subject receives additional preoperative treatment after discontinuing study treatment and prior to surgery, every attempt should be made to collect a tissue sample for the study prior to initiation of the new treatment; in these cases, tissue will still be collected at the time of definitive surgery, as above.

Every effort should be made to provide a core specimen from the surgical sample after treatment. The site pathologist should remove a core samples during the dissection of the surgical specimen (using a 5-mm skin punch biopsy device). The samples should be processed preferably within 1 hour, but may be processed up to 2 hours of removal from the patients. This core specimen should be fixed in formalin and processed separately as per the American Society of Clinical Oncology/College of American Pathologists Guideline Recommendations published in Journal of Clinical Oncology 2010⁴².

In the second cohort:

Approximately six core biopsy specimens will be obtained with each biopsy. Alternative to core needle biopsy, fine needle aspirate (FNA) is allowed in this cohort of patients. Cytology cell blocks should be made from FNA specimens using routine institutional cytology protocol. Biopsy should be obtained from soft tissue metastasis such as breast, liver, skin, lung, or intra-abdominal implants. Bone biopsy, paracentesis (ascites), and thoracocentesis (pleural effusion) specimens are not adequate.

Tumor tissue samples from the following time points will be obtained:

1. Pretreatment biopsy (biopsy#1) will be performed within 3 weeks after registration. However, the pretreatment biopsy can be omitted in patients who have recent biopsy but have not been started on breast cancer treatment within 12 weeks prior to the registration and there is adequate tumor tissue sample as per section 3.1.9. (T0-Second cohort)

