10.4 End of Study (Treatment) / Withdrawal

All patients must continue to be observed for 30 days after the last dose of study medication or until death; whichever occurs first. At the end of the study treatment, the following procedures should be performed within 4 weeks.

- Assessment of Concomitant Treatments including medication use
- Physical examination including examination of major body systems, height, body weight, ECOG performance status, and vital signs (temperature, blood pressure, heart rate, respiratory rate)
- Laboratory studies: CBC with diff; chemistries including sodium, potassium, chloride, bicarbonate, BUN, creatinine, glucose, total bilirubin, calcium, total protein, albumin, AST (SGOT), ALT (SGPT) , alkaline phosphatase, LDH, uric acid, phosphorus, and magnesium

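### Section 5.7 stops data collection for consented patients who never start treatment, although section 7.1 counts adverse events from consent, so harm from a pre-dose study biopsy can go unrecorded

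*Combined protocol and SAP*

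**What the plan says.** On data collection:

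- Section 5.7 ends with a rule for two groups, those found ineligible and those who "refuse to start treatment after consenting will not be followed and their information will not be collected". No exception is made for adverse events.
- Section 7.1 defines an adverse event as "any untoward occurrence reflecting a change from baseline state after signing informed consent and up to 30 days from last administration of the study medication". Section 7.1.1 adds that "AEs of any grade will be documented in the case report form".
- Section 7.2 requires expedited IRB reporting of harm that is both unexpected and probably related. Section 7.3 requires any serious adverse event to go to the drug supplier within 24 hours of awareness.
- Section 5.8 requires the reason for removal and its date in the case report form.
- Section 10.4 says "All patients must continue to be observed for 30 days after the last dose of study medication or until death".

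On the biopsy before treatment:

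- Section 4.1 lists the "Signed patient consent form" among the documents needed to register a patient.
- For the second cohort, section 5.1 says "Pretreatment biopsy (biopsy#1) will be performed within 3 weeks after registration", and treatment starts only afterwards. Section 3.1.18 calls the two biopsies research biopsies. It and section 5.1 waive the first one when recent, adequate tissue exists.
- Section 9.1.1 says "Approximately six core biopsy specimens will be obtained with each biopsy". The named sites include liver, lung and intra-abdominal implants. Fine needle aspiration is an accepted alternative.
- Section 3.1.9 requires an additional core biopsy, in either cohort, from patients who agree to take part but lack adequate tissue.
- Both section 10 calendars mark adverse event evaluation for the first time at day 1; the pre-study cell is empty.

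**The concern.** One section opens the safety record at consent. Another closes it, without exception, for consented patients who leave before dosing for either of two reasons. If nothing happened to patients in that interval, this would be a drafting untidiness. But the protocol can place an invasive procedure there, performed for the study and before any drug.

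What is at stake is the record of harm from study procedures. A patient who has a painful or complicated biopsy may decline to go on because of it. Under section 5.7 that decision is what ends collection, so the missing events would not be a random sample of biopsy events. They would come from patients whose biopsy experience may have led them to leave.

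**Working it through.** The plan states no figure on this point and none is needed. The check is to put the provisions in time order and see which one governs a given patient.

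**Sequence for a second-cohort patient who needs biopsy#1**

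1. Consent is signed. The adverse event window opens (7.1).
2. She is registered; consent is part of the registration packet (4.1). Biopsy#1 therefore falls after consent.
3. Biopsy#1 is done up to 3 weeks after registration (5.1, 9.1.1).
4. Day 1: first dose, and the first adverse event evaluation in the calendar.

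The length of step 3 is itself unclear. Sections 4.1 and 10.2 and the visit schedule in section 10 put the start of treatment within 3 business days of registration, while section 5.1 allows the biopsy alone up to 3 weeks. Those passages need to be reconciled.

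**The additional core under 3.1.9** comes after the patient has agreed to take part and is tied to an eligibility criterion, so it belongs to screening. Under section 10.2, eligibility is decided when screening is complete. A patient can therefore have this core and still be found ineligible, or refuse.

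**Two patients with the same biopsy complication**

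| | Starts treatment | Refuses to start, or is found ineligible before dosing |
|---|---|---|
| Inside the 7.1 window at the time of harm | Yes | Yes |
| Reaches the first scheduled evaluation (day 1) | Yes | No |
| Section 5.7 | Followed to 30 days after last dose | Not followed, no information collected |
| End of the 7.1 window | 30 days after last dose | Undefined: there is no last dose |

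The harm is identical. Whether it is recorded depends on whether she stayed.

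**Do other provisions close the gap?**

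- Section 7.3 is not restricted to dosed patients. A serious event that the site knows of must be reported. But 7.3 also expects follow-up and final reports, and 5.7 ends the follow-up through which the outcome, or a later event, would be learned.
- Section 7.2 needs the harm to be unexpected. Under 7.1.2 an event described in the consent form is expected, so a biopsy complication listed there would fall outside 7.2.
- Section 5.8 secures a reason and a date, not the grade, course or outcome of an event.
- A non-serious event in an undosed patient is covered only by 7.1, the provision that 5.7 contradicts.

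**The case against.** The strongest reply is that the affected group is small and already partly covered. Biopsy#1 is waived with recent adequate tissue, fine needle aspiration may replace cores, and the 3.1.9 core is needed only when tissue is inadequate. In the first cohort the original diagnostic sample may serve as baseline. All of this stands: many patients may never have a pre-dose study biopsy.

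Four stronger readings are tempting, and the documents do not support them.

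- **Serious biopsy complications go unreported.** Section 7.3 requires any serious event to be reported. What 5.7 puts at risk is the follow-up of that event, not the duty to report it. A probability of a missed serious event would need a complication rate and a count of patients biopsied but never dosed. The documents give neither.
- **Patients vanish without explanation.** Section 5.8 requires the reason and date of removal. Its note that withdrawing patients count for response only if they received protocol therapy suggests that it also covers untreated patients. This conflicts with 5.7, but it does not leave the reason undocumented by design.
- **Patients treated and later found ineligible leave the safety data.** Section 5.7 sets no time limit on finding a patient ineligible, so a literal reader could infer this. But the sentence pairs ineligibility with refusal to start, which reads more naturally as exit before treatment. Section 10.4 and the opening of 5.7 require 30 days of observation after the last dose. The wording deserves clarification; the loss is not established.
- **The primary safety objective is compromised.** That objective concerns entinostat with anastrozole or tamoxifen, and dose-limiting toxicities must be treatment-related. Undosed patients inform neither.

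It is also fair to say that a patient medically unable to start is not clearly under 5.7 at all; the intercurrent illness criterion in 5.8 fits her at least as well.

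**Conclusion.** The conflict between 5.7 and 7.1 is real, and 5.7 also sits unreconciled with 7.3 and 5.8. A site that follows 5.7 as written would stop recording biopsy harm in consented patients who refuse to start or are found ineligible, while recording the same harm in those who go on to treatment. This is a rule that works against another rule, not merely a missing detail.

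The conclusion is firmest for non-serious events, for events expected under 7.1.2, and for the outcome of serious ones. It applies only where a study biopsy takes place after consent and before the first dose. The number of such patients, and so the size of the loss, cannot be computed from the documents. Drug safety, dose-limiting toxicity and efficacy analyses are unaffected. The importance is modest, but the correction is specific and cheap.

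**What to change.** Four changes of wording:

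1. In section 5.7, limit the no-collection sentence to patients who had no study-specific procedure and received no study drug.
2. For anyone who had a study biopsy, record the reason for not starting and collect adverse and serious adverse events until 30 days after the last study procedure or last dose, whichever is later.
3. In section 7.1, give the adverse event window the same end point, so that it is defined for a patient who is never dosed.
4. In sections 5.7 and 10.4, state that the 30-day follow-up applies to every dosed patient, whatever is later found about eligibility.

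The cost is a few sentences and a short case report form for what should be a few untreated patients. No dose, treatment schedule or planned analysis changes.

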5.8 Criteria for Removal from Study

Patients will be removed from study when any of the criteria listed below applies. The reason for study removal and the date the patient was removed must be documented in the case report form.

- Evidence of rapid disease progression during treatment at the discretion of the treating investigator.
- Non-compliance with the study protocol; including, but not limited to not attending the majority of scheduled visits. The Protocol Chair will determine when non-compliance should lead to removal from study.

Note: The patients will still be included in the overall evaluation of response (intent-to-treat analysis).

- Unacceptable major toxicity or the dosing delay and/or delay in the surgery ≥ 2 weeks.

Note: The patients will still be included in the overall evaluation of response (intent-to-treat analysis).

- Intercurrent illness or condition that would, in the judgment of the treating investigator, affect assessment of clinical status to a significant degree or require discontinuation of study treatment.
- At subject's own request.

Note: The reason for discontinuation from the study must be documented. The patients will be included in the overall evaluation of response (intent-to-treat analysis) if any protocol therapy was administered prior to withdrawal.

- Study is closed for any reason (e.g. new information shows that the patient's welfare would be at risk if she continued study treatment).
- Subject withdraws consent for follow-up.
- Subject is lost to follow-up.
- Study is terminated for any reason.

6. DOSING DELAYS/DOSE MODIFICATIONS

6.1 Recommended Dose Adjustments

Although entinostat and anastrozole/tamoxifen have distinct toxicity profiles, they do share some adverse events such as fatigue and nausea. There is the theoretical possibility that one agent may potentiate the other and hence drug causality will not always be clear. In the event of uncertainty, dose reductions and/or delays will follow the most conservative approach, i.e., withholding both drugs until resolution of the event.

